4.1.7 Anti-drug Antibody (ADA) Response

The serum samples for ADA of VIS649 will be collected at the time points detailed in the Schedule of Assessments in Table 1, and the data of ADA and titers will be analyzed.

4.1.8 Assessment of Response to Tetanus and Diphtheria Vaccination

Data of assessment of response to tetanus/diphtheria vaccination will be collected by subject for cohort 5 only at the time points detailed in the Schedule of Assessments in Table 1.

PAREXEL International
Statistical Analysis Plan

4.2 Analysis Populations

4.2.1 Safety population

All randomized subjects who received at least one dose of study drug. Subjects will be included in the analysis according to the dose and study drug received.

4.2.2 Pharmacokinetic (PK) population

All randomized subjects with at least one quantifiable VIS649 concentration. Subjects will be included in the analysis according to the dose and study drug received.

4.2.3 Pharmacodynamic (PD) population

The safety population subset with at least one PD parameter assessment (IgA, IgG, IgM) post study drug (VIS649 or placebo) dosing. Subjects will be included in the analysis according to the dose and study drug received.

4.3 Statistical Analysis Methods

4.3.1 Listings and Descriptive Statistics

All original and derived parameters will be listed. Listings will be by cohort, dose, subject and, where applicable, time post dose.

All listings will include repeated and unscheduled measurements.

The following rules will apply to any repeated measurements:

- If the repeated measurement occurs prior to the first dose of study drug, then the last obtained value of any repeated measurement will be used in the descriptive statistics.
- If the repeated measurement occurs after the first dose of study drug, then the original value of any repeated measurements will be used in the descriptive statistics.

Frequency counts (number of subjects [n] and percentages) will be presented for each qualitative variable. Descriptive statistics (n, mean, standard deviation [SD], median, minimum and maximum) will be calculated and presented for each quantitative variable (unless otherwise stated).

PAREXEL International Statistical Analysis Plan

The rules with regards to the presentation of the frequency counts (number of subjects [n] and percentages) are as follows: if frequency count is 0, percentage will not be presented; if percentage is 100%, no decimal places will be given.

All descriptive statistics will be presented by treatment (dose). Subjects who receives placebo within cohort 1 - 4 will be presented as pooled placebo group, and subjects receiving placebo within cohort 5 will be used as individual placebo group as well. Data grouped from cohort 1-4, cohort 5 only and overall (all cohorts) may be analysed separately. In addition, a pooled VIS649 group (i.e. all subjects who receive VIS649 regardless of dose) will be presented for demographics, disposition, and adverse event. The baseline for all measurements (where applicable) will be the last pre-dose measurement unless specified.

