4.1.4 Safety Variables

4.1.4.1 Adverse Events

Adverse event reporting will begin for each subject from Baseline (Day -1) and will continue until the End-of-study Visit. All serious adverse events (SAEs) will be recorded from signing of the ICD until the End-of-study Visit.

A treatment-emergent adverse event (TEAE) is defined as an AE that begins or that worsens in severity after at least one dose of the study drug has been administered.

The Principal Investigator will assess all AEs for severity in accordance with the standard ratings: Mild, Moderate and Severe. Details can be found in the section 6.2.1.3.1 of the CSP.

The Principal Investigator will assess the causality/relationship between the study drug and the AE based on the categories of Related, Probably related, Possibly related, Unlikely to be related, and Unrelated. The causality for each AE will be summarized as “related” (Related, Probably related, and Possibly related) and “not related” (Unlikely to be related, and Unrelated). Details are described in the section 6.2.1.3.2 of the CSP.

AEs for cohort 5 will be assessed for relationship to vaccine and its administration separately from relationship to study drug and its administration (see sections 1.3 and 6.2.1.3 of the CSP for details).

All AEs will be coded using the Medical Dictionary for Regulatory Activities (MedDRA) version 21.1 or higher.

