4.3.10 Anti-drug Antibody (ADA) Response Analysis

For cohort 5, if number of either Japanese subjects or non-Japanese subjects is less than 3, cohort 5 won't be included in "by ethnicity" analysis.

[figure not shown]
Anti-VIS649 ADA evaluations will be listed including the confirmatory assay (positive/negative) and titers [Listing 16.2.10.1]. A “titre specific cut-point” might be used to assess titer, another category, for

PAREXEL International

Statistical Analysis Plan

these subjects that are confirmed positive based on the screening cut-point that are not considered positive for titer, might be included in the listing and be footnoted.

[figure not shown]
A summary table of the ADA response (positive or negative) will be presented, by treatment (cohort 1-4 or pooled placebo or cohort 5 or cohort 5 placebo) and by ethnicity and dose separately, based on the Safety Population [Tables 14.3.8.1 and 14.3.8.2]. In addition, the ADA titers (log10) (n, median, minimum and maximum) will be summarized by treatment (cohort 1-4 or pooled placebo or cohort 5 or cohort 5 placebo) and by ethnicity and treatment - separately for all subjects with a positive confirmatory assay at each time point [Tables 14.3.8.3 and 14.3.8.4], this tabulation will include a summary of the highest titer across all time points for each subject.

Following figures will be created for ADA titers.

- Figure 14.2.3.1: Spaghetti Plot of ADA log10 (titer) Over Time (Safety Population). For each dose separately, spaghetti plot of log10 (titer) vs. time, split in pre-Ab negative and pre-Ab positive population will be generated for subjects.
- Figure 14.2.3.2: Mean ADA log10 (titer) Over Time (Safety Population). For each dose separately, line plot of the mean log10 (titer) vs. time, split in pre-Ab negative and pre-Ab positive population will be generated for dose groups.

PAREXEL International
Statistical Analysis Plan

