4.3.11.1 Adverse Events

The following listing and tables will be produced:

- All Pre-treatment and treatment-emergent AE [Listing 16.2.7].
- All Serious AEs (if applicable) [Listing 14.3.2.1].
- All Adverse Events Leading to Discontinuation (if applicable) [Listing 14.3.2.2].

The following information will be included in the listings: Verbatim, system organ class (SOC), preferred term (PT), AE onset date (and time) and study day, AE end date (and time) and duration (days), severity, relationship to IMP, AE outcome, TEAE indicator flag and SAE indicator flag.

An overall summary of all treatment-emergent adverse events [Table 14.3.1.1] will present the number and percentage of subjects, as well as number of events, according to the following categories:

- All treatment emergent adverse events
- Emergent adverse events Related to IMP

PAREXEL International Statistical Analysis Plan

- Mild treatment emergent adverse events
- Moderate treatment emergent adverse events
- Severe treatment emergent adverse events
- Serious treatment emergent adverse events
- Treatment emergent adverse events leading to early termination
- Deaths

Other summary tables for adverse events will include:

- Table 14.3.1.2: Number and Percentage of Subjects with Treatment Emergent Adverse Events by System Organ Class, and Preferred Term
- Table 14.3.1.3: Number and Percentage of Subjects with Treatment Emergent Adverse Events by System Organ Class, Preferred Term, and Severity
- Table 14.3.1.4: Number and Percentage of Subjects with Treatment Emergent Adverse Events “Related to IMP” by System Organ Class, Preferred Term, and Severity
- Table 14.3.1.5: Number and Percentage of Subjects with Treatment Emergent Adverse Events “Not Related to IMP” by System Organ Class, Preferred Term, and Severity

If a subject has multiple AEs with the same preferred term but occurring after each dose administration, then one AE will be counted for each treatment.

Adverse event summaries will be ordered in terms of decreasing frequency for SOC, and PT within SOC, and then alphabetically for SOC, and PT within SOC.

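### Minor: the mandatory pooled VIS649 adverse event column (planned n=38) includes 10 vaccinated cohort 5 subjects, while the pooled placebo column (planned n=8) includes none

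*SAP*

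**What the plan says.** SAP 4.3.1 sets the summary groups. Descriptive statistics are presented by treatment (dose). On the placebo side, "Subjects who receives placebo within cohort 1 - 4 will be presented as pooled placebo group". The cohort 5 placebo recipients are kept apart as a group of their own. On the active side, "a pooled VIS649 group (i.e. all subjects who receive VIS649 regardless of dose) will be presented for demographics, disposition, and adverse event". A split by cohort block is permitted but not required: "Data grouped from cohort 1-4, cohort 5 only and overall (all cohorts) may be analysed separately".

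SAP 3.1 and Table 2 give 7 VIS649 and 2 placebo subjects in each of cohorts 1-4, and 10 VIS649 and 5 placebo subjects in cohort 5. Everyone in cohort 5 is also vaccinated. In Table 1 vaccination comes after study drug, and the marked Week 4 samples are taken before it.

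SAP 4.1.4.1 defines a TEAE as "an AE that begins or that worsens in severity after at least one dose of the study drug has been administered", with no exclusion for events after vaccination. It adds that "AEs for cohort 5 will be assessed for relationship to vaccine and its administration separately from relationship to study drug". SAP 4.3.11.1 lists the AE tables (14.3.1.1 to 14.3.1.5). They classify relationship to IMP only, and their columns are not named. For ADA, by contrast, SAP 4.3.10 names the groups: "cohort 1-4 or pooled placebo or cohort 5 or cohort 5 placebo".

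**The concern.** Within one paragraph, SAP 4.3.1 separates cohort 5 on the placebo side and merges it on the active side. The pooled VIS649 column therefore carries vaccine exposure that the pooled placebo column lacks. Vaccine reactions in cohort 5 can raise the any-TEAE, severity, SOC/PT and not-related-to-IMP rows on the active side only.

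The primary endpoint (SAP 2.1) is the proportion of subjects with AEs and SAEs after VIS649. With 7 subjects per dose in cohorts 1-4, readers will naturally look at the pooled column, and the pooled placebo is the obvious column to set beside it. An excess caused by the vaccine could then be read as an effect of VIS649. The plan makes the unmatched column mandatory and leaves the matched one optional.

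The AE section also does not say whether cohorts 3 and 5, which share the 6.0 mg/kg dose, have separate columns. The treatment labels in Table 2 suggest that they do.

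**Working it through.** **Counts (SAP 3.1, 3.2 and Table 2).** The plan's own total is reproduced first: 4×7 + 10 + 4×2 + 5 = 51, as in SAP 3.2. The SAP does not state the pooled sizes; they follow by addition.

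| Group | Planned n | Vaccinated |
|---|---|---|
| Pooled VIS649, all cohorts | 4×7 + 10 = 38 | 10/38 = 26.3% |
| Pooled placebo, cohorts 1-4 | 4×2 = 8 | 0 |
| VIS649, cohorts 1-4 | 4×7 = 28 | 0 |
| Cohort 5 VIS649 | 10 | 10/10 |
| Cohort 5 placebo | 5 | 5/5 |
| All placebo | 8 + 5 = 13 | 5/13 = 38.5% |

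The last row shows that pooling all placebo would not restore balance: 38.5% vaccinated against 26.3%.

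**Expected shift with no drug effect.** Let *b* be the probability of a background AE and *v* the probability of a vaccine reaction reported as an AE. Neither is in the documents. I assume *b* = 20-60% and *v* = 10-70%.

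If the two are independent, the any-TEAE rate in vaccinated subjects is p = 1 − (1−b)(1−v). Pooled VIS649 minus pooled placebo is then (10/38)·v·(1−b), and the expected number of extra subjects is 10·v·(1−b).

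| b | v | Difference (points) | Extra subjects of 38 |
|---|---|---|---|
| 0.6 | 0.1 | +1.1 | 0.4 |
| 0.4 | 0.5 | +7.9 (47.9% vs 40.0%) | 3.0 |
| 0.2 | 0.7 | +14.7 | 5.6 |

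Without independence, p lies between max(b, v) and min(1, b+v). At b = 0.4 and v = 0.5 the difference runs from (10/38)×0.10 = +2.6 to (10/38)×0.50 = +13.2 points. Over the whole assumed range it runs from 0 to (10/38)×0.70 = +18.4 points.

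**Shift against sampling noise.** SE = √{[28b(1−b) + 10p(1−p)]/38² + b(1−b)/8}. At b = 0.4, v = 0.5 and p = 0.7 this is 19.0 points, so the shift is 7.9/19.0 = 0.42 SE. Over the range it is 0.06 to 0.94 SE under independence. Without independence it reaches at most about 1.2 SE (b = 0.2, v = 0.7, p = 0.9).

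**Related-to-IMP rows.** Table 14.3.1.4 and the row "Emergent adverse events Related to IMP" of the overall summary do not shift if an event is attributed to the vaccine alone.

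**With cohort 1-4 columns.** In 28 versus 8, neither group is vaccinated, so the shift from this source is 0.

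**The case against.** The strongest defence is that nothing is computed wrongly or concealed. The summaries are descriptive, no pooled contrast or test is planned, and the SAP never names the pooled placebo as comparator for the pooled VIS649 group. That group can be read as an all-exposed summary, which suits an endpoint defined on subjects given VIS649. By-treatment columns are already required, with cohort 5 placebo shown separately, and Table 2 labels the cohort 5 arms as plus vaccine. Each subject receives one dose, so the n=28 counts can be obtained by adding four columns. The SAP already permits the cohort split, and relationship to vaccine is assessed separately. The size rests on assumed rates, and the range without independence includes zero.

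All of this stands, and it sets the grade at minor. The SAP gives table titles without column layouts, so a matched column might still appear in the outputs. The supplied protocol also describes an optional fifth cohort without vaccine, whereas the SAP follows CSP Amendment 2, Version 3.0, so the SAP governs here.

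The mismatch itself remains. The required pooled active column mixes vaccinated and unvaccinated subjects, the required pooled placebo column does not, and no matched pooled column is required.

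**Conclusion.** The concern holds, as a minor point of comparability. By planned numbers, 26% of the pooled VIS649 group is vaccinated against none of the pooled placebo group. Under the assumed rates with independence and no drug effect, the any-TEAE row would favour placebo by 1.1 to 14.7 points, or by 0 to 18.4 points with any overlap between background and vaccine events. That is small against the sampling error of a comparison with 8 placebo subjects, but it is systematic and avoidable. No formal result is affected. The counts are planned sizes and may change, because cohort 5 enrols up to 15 and withdrawn subjects may be replaced.

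**What to change.** In SAP 4.3.1, make the cohort 1-4 and cohort 5 groupings mandatory for AEs by changing *may* to *will*. In SAP 4.3.11.1, name the columns of Tables 14.3.1.1 to 14.3.1.5 as SAP 4.3.10 does for ADA:

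- pooled VIS649 from cohorts 1-4 (n=28) beside the cohort 1-4 pooled placebo (n=8);
- cohort 5 VIS649 plus vaccine (n=10) beside cohort 5 placebo plus vaccine (n=5);
- the all-exposed VIS649 column (n=38), retained with a footnote that it includes 10 vaccinated subjects and is not matched to the pooled placebo.

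As a separate and optional addition, summarise the relationship to vaccine already collected for cohort 5 in Table 14.3.1.1. The matching does not depend on it.

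The cost is one column, one footnote and, if adopted, one row for cohort 5. The n=38 column should stay because it gives the tighter bound when no events are seen: the one-sided 95% upper limit, 1 − 0.05^(1/n), is 7.6% at n=38 and 10.1% at n=28. Precision against placebo hardly changes. At a common rate of 40%, the SE of the difference is √[0.24(1/28 + 1/8)] = 19.6 points for 28 versus 8, against √[0.24(1/38 + 1/8)] = 19.1 points for 38 versus 8.

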4.3.1.1 Rounding Conventions for Safety Data

The following rules will be followed with regards to the number of decimal places and presentation of data in the tables and listings of safety data:

- All data will be listed according to the number of decimal places presented in the source data.
- Mean and median will be tabulated to one more decimal place than the source data.
- Minimum and maximum values will be tabulated to the same number of decimal places as the source data.
- Standard deviation (SD) will be tabulated to two more decimal places than the source data.
- Coefficient of variation (CV)%, if applicable, will be presented to one decimal place.
- A maximum of three decimal places will apply to all summary statistics.

4.3.1.2 Rounding Conventions for Pharmacokinetic Data

PK Concentration Data:

The following rules will be followed with regards to the number of decimal places and presentation of data in tables and listings of concentration data:

- Source PK concentrations data shall be displayed in $\mu\text{g}/\text{mL}$ without prior rounding

PAREXEL International Statistical Analysis Plan

- The mean, standard deviation (SD), geometric mean and median will be tabulated to one more significant digit compared to the source data, but with a maximum of four significant digits.
- Minimum and maximum values will be tabulated to the same precision as the source data, but with a maximum of three significant digits.
- Geometric coefficient of variation (CV) % and coefficient of variation (CV%) will be presented to one decimal place.

PK Parameter Data:

The following rules will be followed with regards to the number of decimal places and presentation of data in tables and listings of concentration data:

Individual PK Parameters	AUC _{0-112d} AUC _{0-last} AUC _{0-inf}	C _{max}	T _{max}	λ _z	t _{1/2}	CL	V _d
Decimal place for listing	0	2	2	4	1	2	0
Unit	h*ug/ mL	ug/mL	h	1/h	h	mL/h	mL

- The mean, geometric mean, median and SD values will be reported to four significant digits, all other descriptive statistics will be reported to three significant digits except for CV% which will be presented to one decimal place.
- For tmax the minimum and maximum will be presented to two decimal places and all other descriptive statistics will be presented to three decimal places.
- Summary statistics will be calculated from unrounded estimates.

4.3.2 Statistical Significance Level

All statistical tests will be performed at the 5% level of significance and confidence intervals (CI) will be two-sided at the stated coverage probability.

PAREXEL International

Statistical Analysis Plan

4.3.3 Software

All statistical analyses will be performed using Statistical Analysis Software (SAS[®]) Version 9.2 or later. The PK analysis will be performed using WinNonlin Professional Software Version 8.0 or later.

4.3.4 Missing Data

There will be no imputation of missing data done except for defining Treatment Emergent Adverse Event (TEAE) and for defining prior and concomitant classification.

4.3.4.1 Imputation of Partial Start Dates and Times in defining TEAE data:

Any AEs with incomplete start dates/times will be handled according the following rules for classification as treatment-emergent respectively. Such imputations will only be performed for these classifications:

- Adverse events with completely unknown start dates will be imputed with the date of dosing, unless the end date is known and prior to dosing; in that case the start date will be imputed as the date of Screening. Any AEs begin or worsen in severity on Day 1 are TEAEs.
- Adverse events with partially known start dates/times will be treated as follows:
 - Adverse events with unknown start times (but where the date is known) and where the start date is different to the dosing date, will be imputed with a time of 00:00 h for calculations. If the start date is the same as the dosing date the start time will be imputed to the dose time, so the AE is reported as treatment emergent.
 - If only the day is missing, then the day will be imputed with the first day of the month, unless the month and year in which the AE started is a month and year in which the study drug was administered, then the day will be imputed with the first day on which the study drug was administered in that month. If this results in a start date after the end date then the day will be imputed with the first day of the month.
 - If only the month is missing and the year is a year in which the study drug was administered, then the month will be imputed with the first month in which the study

PAREXEL International Statistical Analysis Plan

drug was administered. If this results in a start date after the end date of the AE then the month will be imputed with JAN. If the known year part is not a year in which the study drug was administered then the month will also be imputed with JAN.

- If both the day and month is missing and the year is a year in which the study drug was administered then the day and month will be imputed with the day and month of dosing. If this results in a start date after end date then the day and month will be imputed with 01JAN. If the year is not a year in which the study drug was administered then the day and month will also be imputed with 01JAN.
- If only the year is missing then the year will be imputed with the year of dosing.

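### The SAP's AE start-date rules for a missing month or a missing year are not checked against the dosing date, so some post-dose events would be classed as pre-treatment and leave the AE tables

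*SAP*

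**What the plan says.** SAP 4.3.4.1 states its purpose: "Any AEs with incomplete start dates/times will be handled according the following rules for classification as treatment-emergent respectively". The rules that matter here are these.

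- **Month missing, day and year known.** The condition reads "If only the month is missing and the year is a year in which the study drug was administered". The dosing month is inserted and the recorded day is kept. The only check is against the end date: "If this results in a start date after the end date of the AE then the month will be imputed with JAN". For a known year other than the dosing year, January is used as well.
- **Year missing.** "If only the year is missing then the year will be imputed with the year of dosing". No check follows.
- **Day and month both missing, dosing year known.** "then the day and month will be imputed with the day and month of dosing".
- **Start date wholly unknown.** The dosing date is used, unless a known end date precedes dosing.
- **Date equal to the dosing date, time missing.** The dose time is used, expressly so that the event counts as treatment-emergent.

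SAP 4.1.4.1 defines a treatment-emergent event (TEAE) as "an AE that begins or that worsens in severity after at least one dose of the study drug has been administered". It starts AE reporting at Day -1 and SAE recording at consent. Under SAP 4.3.11.1, Tables 14.3.1.1 to 14.3.1.5 summarise TEAEs only. Listing 16.2.7 also shows pre-treatment events. Listings 14.3.2.1 (SAEs) and 14.3.2.2 (AEs leading to discontinuation) carry no TEAE restriction.

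**The concern.** When the date is uncertain, most of this section leans towards calling the event treatment-emergent. SAP 4.3.4.2 leans the same way: missing severity becomes severe and missing causality becomes related. The month and year rules lack that safeguard, because the imputed date can fall before dosing and nothing brings it back.

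The result is also inconsistent within the section. An AE with only its year recorded is placed on the dosing date and counted. The same AE with its day recorded as well can be placed before dosing and not counted, so more information gives a less cautious classification.

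The primary endpoint in SAP 2.1 is the proportion of subjects with AEs and SAEs after administration. The only planned AE summaries are the five TEAE tables, so an event wrongly classed as pre-treatment is missing from every count that supports that endpoint.

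**Working it through.** The plan gives no figure of its own to reproduce. The dosing dates below are assumed, because the documents give none.

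**Inputs**
- Follow-up: 112 days, extendable to Week 24, i.e. 168 days (Protocol 3.1; SAP Table 1).
- Collection starts at Day -1 for AEs and at consent for SAEs (SAP 4.1.4.1).
- Screening opens at Day -28 (SAP Table 1).
- Active subjects per dose group in cohorts 1-4: 7 (SAP Table 2).

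**Month rule, one case.** Dosed 20 March 2019, true onset 5 April 2019, month missing. Imputed start: 5 March 2019, which is 15 days before dosing. A non-serious AE cannot have that date, because reporting starts on 19 March. An SAE could, because 5 March lies in the screening window.

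For this dosing date every onset on days 1 to 19 of a later month fails. Over 112 days (to 10 July) that is 19 + 19 + 19 + 10 = 67 of 112 days. Over 168 days (to 4 September) it is 5 × 19 + 4 = 99 of 168.

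**Year rule, one case.** Dosed 10 December 2018, true onset 15 January 2019, year missing. Imputed start: 15 January 2018, which is 329 days before dosing. Only the 21 days left in December are classified correctly, so 112 − 21 = 91 of 112 onset days fail, or 168 − 21 = 147 of 168.

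**Averages.** Apply the rules literally to every dosing date in a 365-day year and every onset from 1 to F days after dosing, with equal weight.

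| | F = 112 | F = 168 |
|---|---|---|
| Dosing-onset pairs, 365 × F | 40,880 | 61,320 |
| Month missing: imputed before dosing | 15,174 (37%) | 20,838 (34%) |
| Year missing: imputed before dosing | 6,328 (15%) | 14,196 (23%) |

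The year figure has a closed form. With r days left in the year after dosing, F − r onset days fail when r < F. Summing over r gives F(F + 1)/2, which is 112 × 113/2 = 6,328 and 168 × 169/2 = 14,196.

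- The year rule fails only when follow-up crosses a year end: dosing on or after 11 September (112 days) or 17 July (168 days).
- The month rule cannot fail for December dosing. A later-year onset goes to January of that later year, which is after dosing.
- For about 94% of the month failures, Day -1 does not share the recorded day and year, so a non-serious AE must have begun after dosing.
- About 1% of month-missing pairs give an impossible date, such as day 31 in a 30-day month. These are not counted as failures above.

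**The January fallback is not the fault.** It applies when the AE ended before the imputed start. The true onset then lay in an earlier month, before dosing.

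**Effect on a proportion.** Losing the only TEAE of one subject among 7 changes the proportion by 1/7 = 14 percentage points. If the subject has another TEAE, the overall proportion does not change.

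**The case against.** The best defence is that these records will hardly ever arise. Protocol 6.2.1.2 asks for the onset date and treats only the time as optional. There is one centre with real-time electronic capture (Protocol 9.3). AE checks are at most two weeks apart through Week 16, and queries are resolved before lock. A record with a day and a year but no month would be unusual. This stands, and it is why the point is minor.

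Three stronger readings are tempting, and the documents do not support them.

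- **The error always lowers the AE proportion.** A subject with another TEAE still counts. The month rule can also err the other way: dosed 5 March, screening SAE on 20 February, month missing, gives 20 March and a TEAE, provided a known end date does not precede 20 March.
- **Every affected event must have begun after dosing and survives only in Listing 16.2.7.** SAEs are recorded from consent, so a pre-dose SAE date can be genuine. SAEs and discontinuation AEs also appear in Listings 14.3.2.1 and 14.3.2.2.
- **About half of month-missing onsets fail.** Counting calendar days gives 19/30 = 63% for dosing on the 20th and 14.5/30 = 48% on average. That count ignores onsets in the rest of the dosing month and onsets in a later year, both of which the rule places after dosing.

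Nor are the two rules the reverse of their neighbours. The month rule also anchors on dosing and gives the right class when the recorded day is later than the dosing day. It is an incomplete safeguard.

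**Conclusion.** The point holds as a minor defect. Followed literally, SAP 4.3.4.1 dates some post-dose onsets before dosing and removes them from all five AE summary tables, against the approach of the rest of the section.

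The shares of 37% or 34% (month) and 15% or 23% (year) apply only to post-dose AEs with exactly that date part missing. They assume uniform dosing and onset dates. Whether any follow-up crosses a year end is also an assumption. The likely number of affected records is small, possibly none. If one occurs, it can matter in a group of 7, but only for a subject with no other TEAE.

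**What to change.** Add a closing rule to SAP 4.3.4.1:

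> If the imputed start is before dosing, and the recorded date parts, the AE end date and the AE collection window (Day -1 for AEs, consent for SAEs) do not rule out onset on or after dosing and by end of study, the start is set to the date and time of dosing and the AE is treatment-emergent.

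Replace the missing-year rule with: choose the year that places onset between the start of collection (consent for SAEs, Day -1 for other AEs) and the end-of-study visit. From Day -28 to Week 24 is about 28 + 168 = 196 days, well under a year, so at most one year can fit.

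The start of collection must differ for SAEs. A rule that took the earliest year giving an onset on or after Day -1 would move a screening SAE of 5 March, with dosing on 20 March 2019, to 5 March 2020, beyond Week 24. The current rule dates that SAE correctly.

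The cost is two SAP sentences and a few lines of programming before database lock. No data collection changes, and the imputed dates would still be used only for classification.
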